6.3. Study Period

6.3.1. Interim Visits between Day 1 and End of Treatment

Patients will receive the study drug (Aromasin®) as outpatients and are generally expected to return to the clinic for interim visits at approximately 6 month intervals. Since this study was originally configured as an observational study, patient visits during the course of the study may occur at the discretion of the Investigators according to local clinical practice guideline and/or the Investigator's clinical judgment.

A final End-of-Treatment/Early Termination Visit is required for all study subjects.

The following data will be collected at each study period visit:

- Symptoms;
- Physical examination including major body systems, ECOG performance status, body weight, and vital signs.
- Investigations (as available):
 - Serum Chemistry: total bilirubin, ALT, AST, alkaline phosphatase, GGT, total protein, albumin, BUN, creatinine, uric acid, glucose;
 - Serum FSH and E2;
 - Lipid Profile: Serum HDL-C, LDL-C, total cholesterol, triglycerides;
 - Bone mineral density estimations;
 - Abdominal/transvaginal ultrasonography: Uterine hyperplasia, polyps, fibroids;
 - Breast ultrasonography;
 - Breast mammogram.
- Details of Aromasin® treatment:
 - Dose and duration;
 - Reason for dose change or a missed medication.
- Adverse events/ Serious adverse events.
- Concomitant drug and non-drug treatment (study period):
 - Change in concomitant drug and non-drug treatment including any change in supportive therapy (calcium, bisphosphonates, etc).

6.3.2. Final Visit

For each subject, the final visits will occur at completion the study drug or at the occurrence of any of the events signifying treatment termination (refer [Section 7.2](#)).

Observational Parameters collected at the Final Visit are identical to the Study Period Visits; with the addition of recurrence time and location, if the subject has recurrence.

6.4. Subject Withdrawal

When subjects are permanently withdrawn from treatment, the primary reason for discontinuation must be provided. Reasons for discontinuation include:

- Death due to any cause;
- Unacceptable toxicity;
- Disease recurrence/ metastases;
- Appearance of a second primary or contralateral breast cancer;
- Protocol deviation (eg, subject noncompliance, including the study drug accumulated dosage subject taken is less than 70% or more than 130% of the total study drug dosage);
- Receive other aromatase inhibitors (not Aromasin®);
- Withdrawal of subject consent;
- Study terminated by sponsor;
- Other reason.
- Patients may withdraw from the study at any time at their own request, or they may be withdrawn at any time at the discretion of the investigator.
- Withdrawal of Consent: Subjects who request to discontinue study treatment will remain in the study and must continue to be followed for protocol specified follow-up procedures. The only exception to this is when a subject specifically withdraws consent for any further contact with him/her or persons previously authorized by subject to provide this information. Subjects should notify the investigator, in writing, of their decision to withdraw consent from future follow-up, whenever possible. The withdrawal of consent should be explained in detail in the medical records by the investigator, as to whether the withdrawal is from further treatment with study drug only or also from study procedures and/or post treatment study follow-up, and entered on the appropriate CRF page. In the event that vital status (whether the subject is alive or dead) is being measured, publicly available information should be used to determine vital status only as appropriately directed in accordance with local law.
- If the patient withdraws consent, no further evaluations should be performed and no additional data should be collected. The sponsor may retain and continue to use any data collected before such withdrawal of consent.

- Lost to Follow-Up:
 - If a subject does not return for a scheduled visit, every effort should be made to contact the subject. All attempts to contact the subject and information received during contact attempts must be documented in the subject's medical record. In *all* circumstances, every effort should be made to document subject outcome. The investigator should inquire about the reason for withdrawal and follow-up with the subject regarding any unresolved adverse events.
 - All reasonable efforts must be made to locate subjects to determine and report their ongoing status. This includes follow-up with persons authorized by the subject as noted above. Lost to follow-up is defined by the inability to reach the subject after a minimum of three documented phone calls, faxes, or emails as well as lack of response by subject to one registered mail letter. All attempts should be documented in the subject's medical records. If it is determined that the subject has died, the site will use permissible local methods to obtain the date and cause of death. If investigator's use of third-party representative to assist in the follow-up portion of the study has been included in the subject's informed consent, then the investigator may use a Sponsor retained third-party representative to assist site staff with obtaining subject's contact information or other public vital status data necessary to complete the follow-up portion of the study. The site staff and representative will consult publicly available sources, such as public health registries and databases, in order to obtain updated contact information. If after all attempts, the subject remains lost to follow-up, then the last known alive date as determined by the investigator should be reported and documented in the subject's medical records.

7. ASSESSMENTS

Data to be collected on the case report forms must be documented in patient records.

7.1. Efficacy Endpoint

The first occurrence of any of the following events constitutes an efficacy endpoint for the subject:

- Loco-regional/distant recurrence of the primary breast cancer;
- Appearance of a second primary or contralateral breast cancer;
- Death due to any cause.

Loco-regional recurrence is defined as any recurrence in the ipsilateral breast, chest wall or axillary lymph nodes.

7.2. Safety Parameters

The safety of treatment with Aromasin® will be assessed by Adverse Event reporting in the study. Every adverse event that is observed must be recorded as an adverse event in the CRF, whether or not the Investigator suspects a causal relationship with study drug.

Adverse events of particular interest in this study:

- Gynaecological: Bleeding, discharge, uterine dilatation and curettage;
- Cardiac: myocardial infarction, hypertension;
- Venous thromboembolic events;
- Musculoskeletal: Joint stiffness, arthralgia, muscle cramps, fractures;
- Menopausal symptoms: Hot flushes, anxiety, depression, headaches;
- Changes in lipids;
- Changes in bone mineral density.

Severity of the adverse events reported while on Aromasin® will be graded by the National Cancer Institute Common Terminology Criteria for Adverse Events [CTCAE] version 3.0.

Please refer to the [Section 8](#) for additional details on recording and reporting of adverse events.

7.3. Pregnancy Testing

Not applicable for this Aromasin® pragmatic clinical trial because the use of Aromasin® for this indication is for post-menopausal women.

8. ADVERSE EVENT REPORTING

8.1. Adverse Events

All observed or volunteered Adverse Event (AEs) regardless of treatment group or suspected causal relationship to the investigational product(s) will be reported as described in the following sections.

For all AEs, the investigator must pursue and obtain information adequate both to determine the outcome of the AE and to assess whether it meets the criteria for classification as a serious adverse event (SAE) requiring immediate notification to Pfizer or its designated representative. For all AEs, sufficient information should be obtained by the investigator to determine the causality of the AE. The investigator is required to assess causality.

Follow-up by the investigator may be required until the event or its sequelae resolve or stabilize at a level acceptable to the investigator, and Pfizer concurs with that assessment.

As part of ongoing safety reviews conducted by the sponsor, any nonserious AE that is determined by the sponsor to be serious will be reported by the sponsor as an SAE. To assist in the determination of case seriousness, further information may be requested from the investigator to provide clarity and understanding of the event in the context of the clinical study.

8.2. Reporting Period

For SAEs, the active reporting period to Pfizer or its designated representative begins from the time that the subject provides informed consent, which is obtained prior to the subject's participation in the study, ie, prior to undergoing any study-related procedure and/or receiving investigational product, through and including 28 calendar days after the last administration of the investigational product. SAEs occurring to a subject after the active reporting period has ended should be reported to the sponsor if the investigator becomes aware of them; at a minimum, all SAEs that the investigator believes have at least a reasonable possibility of being related to study drug are to be reported to the sponsor.

AEs (serious and nonserious) should be recorded on the Case Report Form (CRF) from the time the subject has taken at least 1 dose of study treatment through the last subject visit.

- If a patient begins a new anticancer therapy, the AE reporting period for nonserious AEs ends at the time the new treatment is started. Death must be reported if it occurs during the SAE reporting period after the last dose of investigational product, irrespective of any intervening treatment.

8.3. Definition of an Adverse Event

An AE is any untoward medical occurrence in a clinical investigation subject administered a product or medical device; the event need not necessarily have a causal relationship with the treatment or usage. Examples of AEs include but are not limited to:

- Abnormal test findings;
- Clinically significant symptoms and signs;
- Changes in physical examination findings;
- Hypersensitivity;
- Progression/worsening of underlying disease;
- Drug abuse;
- Drug dependency.

Additionally, they may include the signs or symptoms resulting from:

- Drug overdose;
- Drug withdrawal;
- Drug misuse;
- Drug interactions;
- Extravasation;
- Exposure during pregnancy (EDP);
- Exposure via breastfeeding;
- Medication error;
- Occupational exposure.
- Worsening of signs and symptoms of the malignancy under study should be reported as AEs in the appropriate section of the CRF. Disease progression assessed by measurement of malignant lesions on radiographs or other methods should not be reported as AEs.

8.4. Medication Errors

Medication errors may result, in this study, from the administration or consumption of the wrong drug, by the wrong subject, at the wrong time, or at the wrong dosage strength. Such medication errors occurring to a study participant are to be captured on the adverse event (AE) page of the case report forms (CRFs) and on the SAE form when appropriate. In the event of medication dosing error, the sponsor should be notified immediately.

Medication errors are reportable irrespective of the presence of an associated AE/SAE, including:

- Medication errors involving subject exposure to the investigational product;
- Potential medication errors or uses outside of what is foreseen in the protocol that do or do not involve the participating subject.

Whether or not the medication error is accompanied by an AE, as determined by the investigator, the medication error and, if applicable, any associated AE(s) are captured on an AE CRF page (refer to the ADVERSE EVENT REPORTING section for further details).

8.5. Abnormal Test Findings

The criteria for determining whether an abnormal objective test finding should be reported as an AE are as follows:

- Test result is associated with accompanying symptoms; and/or
- Test result requires additional diagnostic testing or medical/surgical intervention; and/or
- Test result leads to a change in study dosing or discontinuation from the study, significant additional concomitant drug treatment, or other therapy; and/or
- Test result is considered to be an AE by the investigator or sponsor.

Merely repeating an abnormal test, in the absence of any of the above conditions, does not constitute an AE. Any abnormal test result that is determined to be an error does not require reporting as an AE.

8.6. Serious Adverse Events

An SAE is any untoward medical occurrence at any dose that:

- Results in death;
- Is life-threatening (immediate risk of death);
- Requires inpatient hospitalization or prolongation of existing hospitalization;
- Results in persistent or significant disability/incapacity (substantial disruption of the ability to conduct normal life functions);
- Results in congenital anomaly/birth defect.
- Progression of the malignancy under study (including signs and symptoms of progression) should not be reported as an SAE unless the outcome is fatal within the safety reporting period. Hospitalization due to signs and symptoms of disease progression should not be reported as an SAE. If the malignancy has a fatal outcome during the study or within the safety reporting period, then the event leading to death must be recorded as an AE and as an SAE with Common Terminology Criteria (CTC) Grade 5 (see section on Severity Assessment).
- Lack of efficacy should be reported as an AE when it is associated with an SAE.

Medical and scientific judgment is exercised in determining whether an event is an important medical event. An important medical event may not be immediately life-threatening and/or result in death or hospitalization. The important medical event should be reported as serious, if it is determined that the event may jeopardize the subject or may require intervention to prevent one of the other AE outcomes.

Examples of such events are intensive treatment in an emergency room or at home for allergic bronchospasm; blood dyscrasias or convulsions that do not result in hospitalization; or development of drug dependency or drug abuse.

8.6.1. Protocol-Specified Serious Adverse Events

There are no protocol-specified SAEs in this study. All SAEs will be reported by the investigator as described in previous sections, and will be handled as SAEs in the safety database (see section on Serious Adverse Event Reporting Requirements).

8.6.2. Potential Cases of Drug-Induced Liver Injury

Liver function tests (LFTs) are not required as a routine safety monitoring procedure in this study. However, should an investigator deem it necessary to run LFTs because of clinical sign/symptom presentation in a subject, such LFT results should be handled and followed up as described below.

Abnormal values in aspartate transaminase (AST) and/or alanine transaminase (ALT) levels concurrent with abnormal elevations in total bilirubin level that meet the criteria outlined below in the absence of other causes of liver injury are considered potential cases of drug-induced liver injury (potential Hy's law cases) and should always be considered important medical events.

The threshold of laboratory abnormalities for a potential case of drug-induced liver injury depends on the subject's individual baseline values and underlying conditions. Subjects who present with the following laboratory abnormalities should be evaluated further to definitively determine the etiology of the abnormal laboratory values:

- Subjects with AST or ALT and total bilirubin baseline values within the normal range who subsequently present with AST or ALT values ≥ 3 times the upper limit of normal (X ULN) concurrent with a total bilirubin value ≥ 2 X ULN with no evidence of hemolysis and an alkaline phosphatase value ≤ 2 X ULN or not available.
- For subjects with preexisting ALT **OR** AST **OR** total bilirubin values above the ULN, the following threshold values should be used in the definition mentioned above:
 - For subjects with preexisting AST or ALT baseline values above the normal range: AST or ALT values ≥ 2 times the baseline values and ≥ 3 X ULN, or ≥ 8 X ULN (whichever is smaller).

Concurrent with

- For subjects with preexisting values of total bilirubin above the normal range: Total bilirubin level increased by 1 X ULN **or** ≥ 3 X ULN (whichever is smaller).

The subject should return to the investigational site and be evaluated as soon as possible, preferably within 48 hours from awareness of the abnormal results. This evaluation should include laboratory tests, detailed history, and physical assessment.

In addition to repeating measurements of AST and ALT, laboratory tests should include albumin, creatine kinase, total bilirubin, direct and indirect bilirubin, gamma-glutamyl transferase, prothrombin time (PT)/ international normalized ratio (INR), and alkaline phosphatase. A detailed history, including relevant information, such as review of ethanol, acetaminophen, recreational drug and supplement consumption, family history, occupational exposure, sexual history, travel history, history of contact with a jaundiced person, surgery, blood transfusion, history of liver or allergic disease, and work exposure, should be collected. Further testing for acute hepatitis A, B, or C infection and liver imaging (eg, biliary tract) may be warranted. All cases confirmed on repeat testing as meeting the laboratory criteria defined above, with no other cause for liver function test (LFT) abnormalities identified at the time, should be considered potential Hy's law cases irrespective of availability of all the results of the investigations performed to determine etiology of the abnormal LFTs. Such potential Hy's law cases should be reported as SAEs.

8.7. Hospitalization

Hospitalization is defined as any initial admission (even less than 24 hours) in a hospital or equivalent healthcare facility or any prolongation to an existing admission. Admission also includes transfer within the hospital to an acute/intensive care unit (eg, from the psychiatric wing to a medical floor, medical floor to a coronary care unit, or neurological floor to a tuberculosis unit). An emergency room visit does not necessarily constitute an hospitalization; however, the event leading to the emergency room visit should be assessed for medical importance.

Hospitalization does not include the following:

- Rehabilitation facilities;
- Hospice facilities;
- Respite care (eg, caregiver relief);
- Skilled nursing facilities;
- Nursing homes;
- Same-day surgeries (as outpatient/same-day/ambulatory procedures).

Hospitalization or prolongation of hospitalization in the absence of a precipitating, clinical AE is not in itself an SAE. Examples include:

- Admission for treatment of a preexisting condition not associated with the development of a new AE or with a worsening of the preexisting condition (eg, for workup of persistent pre-treatment laboratory abnormality);
- Social admission (eg, subject has no place to sleep);
- Administrative admission (eg, for yearly physical examination);
- Protocol-specified admission during a study (eg, for a procedure required by the study protocol);
- Optional admission not associated with a precipitating clinical AE (eg, for elective cosmetic surgery);
- Hospitalization for observation without a medical AE;
- Preplanned treatments or surgical procedures. These should be noted in the baseline documentation for the entire protocol and/or for the individual subject;
- Admission exclusively for the administration of blood products.

Diagnostic and therapeutic noninvasive and invasive procedures, such as surgery, should not be reported as AEs. However, the medical condition for which the procedure was performed should be reported if it meets the definition of an AE. For example, an acute appendicitis that begins during the AE reporting period should be reported as the AE, and the resulting appendectomy should be recorded as treatment of the AE.

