6.3. Safety Endpoints

Safety endpoints include:

- Adverse events of particular interest are as follows:
 - Gynaecological: Bleeding ,discharge, uterine dilatation and curettage;
 - Cardiac: myocardial infarction, hypertension;
 - Venous thromboembolic events;
 - Musculoskeletal: Joint stiffness, arthralgia, muscle cramps, fractures;
 - Menopausal symptoms: Hot flushes, anxiety, depression, headaches.
- Changes in laboratory parameters, including lipids.
- Changes in bone mineral density.
- Vital signs.

- Reasons for discontinuation of Aromasin[®] therapy.
- Duration of Aromasin[®] therapy.

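### Uterine dilatation and curettage is a named adverse event of interest, but protocol 8.7 bars procedures from AE reporting, so its AE-based count is understated and depends on which section a site follows

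*Protocol*

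**What the plan says.** Protocol 7.2 sets the basis for safety: "The safety of treatment with Aromasin® will be assessed by Adverse Event reporting in the study". It then lists the adverse events of particular interest, the first group being "Gynaecological: Bleeding, discharge, uterine dilatation and curettage". SAP 6.3 repeats that group among the safety endpoints ("Gynaecological: Bleeding ,discharge, uterine dilatation and curettage"). For details of recording, 7.2 sends the reader to Section 8.

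Within Section 8, the closing paragraph of 8.7 reads: "Diagnostic and therapeutic noninvasive and invasive procedures, such as surgery, should not be reported as AEs". The next sentence says what to record instead: "However, the medical condition for which the procedure was performed should be reported if it meets the definition of an AE". The worked example there is an appendectomy, which is entered as the treatment of the appendicitis and not as an event itself. No exception is made for D&C or for any other item on the 7.2 list.

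One other source bears on this. At each study-period visit, protocol 6.3.1 collects "Change in concomitant drug and non-drug treatment including any change in supportive therapy".

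**The concern.** D&C is the only item in the gynaecological group that is a procedure. It is named as an endpoint in one place, and the rule for filling in the AE page excludes it in another. Sites are given two instructions for the same event, and nothing in the readable text says which prevails.

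At stake is the meaning of the reported figure. The study is described as a post-approval safety study, with safety as its secondary objective. A low D&C count in the table of events of interest could be taken as a finding about the drug when it partly reflects how sites filled in the form.

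**Working it through.** There is no figure in the plan to reproduce, and the point rests on no sample size, power or event rate. The check is a comparison of the passages.

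**Step 1: the stated source of the count.** Protocol 7.2 bases safety on AE reporting, and SAP 6.3 places D&C under adverse events of particular interest. As written, the count comes from AE records.

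**Step 2: what each instruction produces for one woman who has a D&C.**

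| | Site follows the 7.2 list | Site follows 8.7 |
|---|---|---|
| D&C on the AE page as an event | Yes | No |
| Underlying condition on the AE page | Yes, if it is an AE | Yes, if it is an AE |
| D&C recorded as treatment | Possibly | Yes |
| Adds to the AE-based D&C count | 1 | 0 |

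**Step 3: the pooled count.** Let D be the number of women who have a D&C and p the share of them at sites that enter it as an AE. Then:

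AE-based count = p × D, with 0 ≤ p ≤ 1.

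The count equals D only if every site sets 8.7 aside (p = 1). It is 0 if every site follows 8.7 (p = 0). The documents give neither p nor D, so the shortfall, (1 − p) × D, cannot be calculated. Its direction is known: it cannot be negative.

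**Step 4: does another AE route bring the D&C back?**

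- *Serious events.* 8.7 does not treat same-day surgery as hospitalization, so a day-case D&C does not enter through that criterion.
- *The underlying condition.* If the indication was bleeding, the woman still appears in the gynaecological group, because bleeding is listed. If it was an abnormal scan that led to surgery, 8.5 makes the finding reportable as an AE. She then appears in the AE data under that condition. In neither case does she add to the D&C item.

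**Step 5: is the information held elsewhere?** It should be. 8.7 directs that the procedure be recorded as treatment of the event, and 6.3.1 collects changes in non-drug treatment. However, the readable SAP has no rule that counts a D&C from either record. SAP 8.2.2 refers only to the sponsor's general data standards for safety summaries.

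**The case against.** The strongest reply is that little is lost. The paragraph that bars the procedure from the AE page also requires the condition to be reported and the procedure to be recorded as its treatment. All observed AEs are to be recorded and all safety data summarised. The study has a single arm, plans no inferential analysis and makes no comparison of D&C rates. A site might also reasonably let a study-specific list that names D&C prevail over general wording placed under a hospitalization heading. Finally, part of SAP 8.2.2 is redacted, and a grouping rule may lie there.

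Much of this stands, and it rules out three stronger readings that a reader might infer:

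- *That D&C cannot be observed, or that cases are lost.* The documents do not support this: the treatment records should hold them.
- *That the count will be zero.* This follows only if every site obeys 8.7, and nothing in the documents shows site practice. Nor are the recording rules shown that applied before the study became interventional in May 2016, so it is unknown how much follow-up fell under the current sentence.
- *That the uterine findings on ultrasonography ("Abdominal/transvaginal ultrasonography: Uterine hyperplasia, polyps, fibroids") should become endpoints to close the gap.* These scans are collected as available, at visits left to the investigator's discretion, and baseline results may be up to 2 years old. A rate of new findings would come from a selected group. It would not repair the conflict over D&C.

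What the reply does not remove is the conflict itself. 7.2 does not override 8.7; it points the reader to Section 8. The readable plan names AE reporting as the source and gives no rule for using another.

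**Conclusion.** The contradiction is real, and the passages must be reconciled. As the readable text stands, the AE-based D&C count is a lower bound on the number of women who had the procedure, and its shortfall depends on how sites resolved the conflict. It should not be reported or read as a rate.

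The effect is confined to one descriptive item among several groups of adverse events of interest. Bleeding and discharge are recorded normally, the underlying conditions still reach the AE data, and the primary endpoint is unaffected. The change is worth making before the final analysis, but the study's main conclusions do not turn on it.

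This rests on two assumptions: that no redacted SAP text already derives D&C from treatment records, and that the CRF, which is not among the documents, identifies a D&C where 8.7 and 6.3.1 say treatments are recorded.

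**What to change.** In SAP 6.3, define the D&C endpoint from both sources. Count a woman once if a D&C appears on the AE page, or as the treatment of an AE (8.7), or in the concomitant non-drug treatment record (6.3.1). Report how many women were identified from each source, so that the effect of the recording rule is visible.

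Optionally, add a note to protocol 8.7 that a D&C, being listed in 7.2, is recorded together with its indication. On its own this would be weaker: enrolment was complete in December 2015, so a new recording rule acts only from its date and could split recording into before and after. The SAP derivation also uses data already collected.

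The cost is a small extra derivation and some review of treatment entries for D&C terms. No new visit, procedure or form is needed. The D&C count may come out higher than from the AE page alone. SAP version 1.2 follows protocol amendment 3 and still describes a non-interventional study, so this change can go into the update that it needs in any case.
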